1. INTRODUCTION

African Americans (AAs) with diabetes (DM) go to the emergency department (ED) twice as often as Whites. About 40% of AAs with DM go to the ED each year, and 24% use the ED as their usual place of care (vs. 13% of Whites). These racial disparities reflect differences in socioeconomic (e.g., education, income), individual (e.g., DM self-care practices), and medical (e.g., access to care) factors. The scientific premise of this randomized controlled trial (RCT) is that limited access to primary care and suboptimal DM self-care are two modifiable risk factors that drive high ED use in AAs with DM.

This Phase-III RCT will compare the efficacy of PREVENT (Preventing and Reducing Emergency Visits in diabetes through Education and Trust) vs. Enhanced Usual Care (EUC) to reduce the number of DM-related ED visits and/or hospitalizations over 12 months (primary outcome), in 230 AAs with diabetes, aged 40 years and older, who are recruited from the ED. Note that only 156 participants were randomized due to the pandemic. PREVENT is a culturally relevant intervention that extends from the ED to the community, and aims to improve access to care and DM self-care (secondary outcomes). Note that recruitment was terminated early due to the pandemic (156 subjects were randomized). A mediation analysis will determine whether changes in access to care and/or DM self-care explain PREVENT's efficacy. A moderation analysis will determine whether participants who reside in low- vs. high-need communities [defined by Community Need Index scores (i.e., an indicator of the built environment)] respond differently to treatment.

PREVENT will begin soon after the participant's index ED visit, when many patients remain uncertain how to manage DM or how to access follow-up care. Community Health Workers (CHWs), who are race-concordant with participants, will: 1) deliver in-home DM education to increase participants' knowledge and skills; 2) use DM-specific Behavioral Activation to improve DM self-care; and 3) facilitate telehealth visits with the participant's primary care physician (PCP) and a DM nurse educator to increase access to care. The control treatment, EUC, is usual medical care that is enhanced with DM self-care education. EUC matches PREVENT in treatment intensity (i.e., 6 in-home sessions over 4 months, and 3 booster sessions over the next 8 months) and delivery of culturally relevant DM education, but does not include DM-specific Behavioral Activation or telehealth visits. The treatment comparison will identify PREVENT's specific efficacy over and above EUC.

This RCT is significant as the population ages and becomes more racially diverse, and as ED use and costs increase. This RCT is innovative because it: 1) tests the first ED-to-community intervention designed to reduce the need for ED care in AAs with DM; 2) assesses both subjective and objective indicators of access to care; and 3) defines the specific characteristics of PREVENT that confer its cultural relevance. If successful, PREVENT will meet Healthy People 2020's twin goals of reducing the personal and societal costs of DM and achieving health equity for all Americans.

The Specific Aims of this RCT are:

Primary Specific Aim: Test the efficacy of PREVENT to reduce the number of incident DM-related ED visits and/or hospitalizations over 12 months (primary outcome) in AAs with DM. Hypothesis: PREVENT will halve the number of incident DM-related ED visits and/or hospitalizations relative to EUC over 12 months.

The Secondary Aims are to:

- 1. Test the efficacy of PREVENT to increase perceived access to care over 12 months (secondary outcome). Hypothesis: PREVENT will increase Patient Satisfaction Questionnaire-18 scores to a greater extent than EUC over 12 months.
- 2. Test the efficacy of PREVENT to increase realized access to care over 12 months (secondary outcome). Hypothesis: PREVENT will increase the number of received Diabetes Quality Metrics (e.g., hemoglobin A1c testing, urine screening) to a greater extent than EUC over 12 months.
- 3. Test the efficacy of PREVENT to improve DM self-care over 12 months (secondary outcome). Hypothesis: PREVENT will increase Diabetes Self-Care Inventory scores to a greater extent than EUC over 12 months.
- 4. Determine if increasing subjective and/or objective indicators of access to care and/or DM self-care mediates PREVENT's reduction of DM-related ED visits and/or hospitalizations. Hypothesis: PREVENT will reduce DM-related ED visits and/or hospitalizations to the extent that it increases subjective and/or objective indicators of access to care and/or improves DM self-care.

The Exploratory Aims are to: 1) determine whether PREVENT reduces "all cause" ED visits/hospitalizations relative to EUC.; 2) determine whether Community Need Index scores, literacy, age, and/or sex moderate treatment effects; 3) determine if PREVENT improves glycemic control (i.e., lowers hemoglobin A1c levels), impacts DM-related health beliefs, reduces depression, and/or improves quality-of-life; 4) identify PREVENT's treatment features that confer its cultural relevance; and 5) estimate PREVENT's costs and net financial benefit to the healthcare system.

2: RESEARCH DESIGN SUMMARY

A. Study Purpose and Rationale: This Phase-III RCT will compare the efficacy of Community Care to Prevent Diabetes Emergencies (PREVENT) vs. Enhanced Usual Care (EUC) to reduce incident DM-related ED visits and/or hospitalizations over 12 months in 230 African Americans with diabetes (aged 40 and older), following an ED visit for a DM-related condition. Note that only 156 participants were randomized.

- B. Study Design: This study is a randomized controlled clinical trial in which the unit of randomization is the person. Participants will be randomized 1:1 to PREVENT (the experimental treatment) or EUC (the control condition).
- C. Sample: The sample will comprise 230 older persons (only 156 were randomized) who meet the following criteria:

Inclusion criteria:

- 1) African American race (self-identified)
- 2) Age ≥ 40 years
- 3) Type 1 or 2 DM
- 4) A recent ED visit

Exclusion criteria:

- 1) Diagnosis of dementia
- 2) Anti-dementia medication use
- 3) Life expectancy less than one year (in the opinion of the evaluating ED physician)
- 4) DSM-V psychiatric disorders other than anxiety or depression (as per EMR)
- 5) Intoxicated
- 6) Suicidal
- 7) In police custody or currently incarcerated
- 8) Undergoing medical clearance for a detox center or any involuntary court or magistrate order
- 9) Lives in assisted living, currently in a rehabilitation facility (other than Jefferson), lives in a nursing home or skilled nursing facility

[figure not shown]
10) Pregnancy

- D. Participant Enrollment: Participants will be recruited from the emergency department (ED) at Thomas Jefferson University and affiliated hospitals.
- E. Informed Consent: Informed consent will be obtained in the ED by the ED Research Coordinators or in patients' homes by a study assessor.
- F. Participant Follow-Up. Participants will be assessed at baseline, 6, and 12 months.

Table 1. Design Summary

Objective	Determine the efficacy of PREVENT to prevent ED visits and	
	hospitalizations among African Americans with diabetes	
Major Eligibility Criteria	1) African American race	
	2) Age ≥ 40 years	
	3) Diabetes	
	4) Recent ED visit	
Randomization Unit	Person stratified by HbA1c level (7.5% - 9% vs. ≥ 9%), ED	
	discharge status (i.e., home vs. hospital admission), and whether	
	or not the participant has a Jefferson PCP	
Treatments	PREVENT (n = 115)	
	EUC (n = 115)	
Recruitment Site	Emergency Department	
Enrollment Site	Emergency Department or participants' homes	
Outcome Measures	Primary: Number of diabetes-related ED visits and	
	hospitalizations over 12 months	
	Secondary: Scores on Patient Satisfaction Questionnaire;	
	number of received diabetes quality metrics; scores on Diabetes	
	Self-Care Inventory	
	Exploratory: Depression; diabetes health beliefs; all cause	
	incident ED visits/hospitalizations; glycemic control; quality of life	
Sample Size	230 (only 156 were randomized due to the pandemic)	
Masking Procedures	This is a single blind study in which the Outcome Assessor will be	
	masked but participants, interventionists, and Primary Care	
	Physicians (PCPs) will not	
Study Visit Schedule	Assessments: Baseline, 6, and 12 months	
	Interventions: 6 in-home sessions of PREVENT or EUC, followed	
	by booster sessions at months 6, 8, and 10	
Length of Follow-up	12 months	

Figure 1. Flow Chart and Study Design

3: ORGANIZATIONAL STRUCTURE

3.2. Other Staff

2 Community Health Care Worker (CHW) Interventionist: To be hired. We will hire a CHW interventionist to deliver the in-home of component of the PREVENT intervention to participants randomized to active treatment. The in-home visits will include providing comprehensive diabetes education, strengthening the patient/PCP relationship, and using Behavioral Activation (BA) to facilitate diabetes-related care goals. The CHW interventionist will also facilitate telehealth visits between study participants and their PCPs and the study nurse ([name]). The CHW PREVENT interventionist will complete treatment documentation forms to record details of each PREVENT participant's treatment goals and progress, the length and date of each treatment session, obstacles to diabetes management, referrals provided, supplies dispensed (e.g., glucometer, pedometer), participants' perceptions of the intervention (e.g., cultural relevance, satisfaction with telehealth), and communication between the CHW and the PCP and nurse. The CHW interventionist will audio record each treatment session. Drs. [name] and [name] will review the recordings to rate the quality of the diabetes education provided and to insure that behavioral activation is being delivered according to

protocol. The CHW interventionist will also attend regular case review meetings with Drs. [name], [name], and [name] for supervisory purposes. A second CHW interventionist will deliver EUC (the control condition). Drs. [name] and [name] will review audio recordings of EUC treatment sessions to rate adherence to the EUC protocol and the quality of the diabetes education provided. The EUC interventionist will attend case review meetings with Drs. [name], [name], and [name]. The EUC case review meetings will be separate from the PREVENT meetings.

4 ED Recruitment Coordinators, To be hired. The ED Recruitment Coordinators will work closely with Drs. [name] and [name] to implement the recruitment protocol in the ED. The ED Research Coordinators will screen the ED computerized medical records to monitor study enrollment and identify potential study participants. They will explain the study to potential participants, obtain informed consent, and administer Part 1 of the baseline assessment. Drs. [name] and [name] will supervise the ED Recruitment Coordinators. Having two ED physicians performing this role will optimize the number of hours that there is direct supervision in the ED.

Outcome Assessor, To be hired. The Outcome Assessor will administer Part 2 of the Baseline assessment and follow-up assessments at 6 and 12 months in participants' homes masked to treatment assignment. The Outcome Assessor will obtain informed consent and administer Part 1 of the Baseline Assessment to participants who do not want to be consented in the hospital. [name] will supervise the Outcome Assessor.

Study Coordinator, [name]. [name] will be responsible for providing assistance to [name] with the overall conduct of the PREVENT trial. In addition, she will assist [name] in managing study data. Specifically, she will: 1) maintain administrative data bases (e.g., participant contact information); (2) manage the payment of participant incentives; and (3) send biweekly reports to the Outcome Assessor and CHW Interventionists to inform them of participants who are due for follow-up assessments and intervention visits. Drs. [name] and [name] will supervise the Research Coordinator.

Research Assistant, To be hired. The Research Assistant will be supported by the Department of Neurology at Jefferson. This person will be responsible for: (1) reviewing participants' medical charts at 6 and 12 months to collect data on current medications, diabetes quality metrics, and recent hospitalizations and ED visits; and (2) listen to audiotapes of data collection visits for quality assurance purposes.

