4.3. Participant costs

All patient costs directly related to study participation will be covered by the trial, and thus there will be no financial burden on study participants. This includes costs associated with HbA1c testing at baseline and follow-up assessments, DM educational materials, and supplies to assist with the achievement of treatment goals for PREVENT participants (e.g., glucometers and supplies, pedometers, materials to record glucose readings and daily food intake).

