Cultural Relevance Rating Form	Participants rate the cultural appropriateness of the intervention	At the end of session 6 and the last booster session via phone calls from study staff
ED Visit Form	Record participant's perception of their recent ED visit	Session 1
EMR Check Form	To find out about medication changes and new health problems	Prior to each booster session
Family/Friend Involvement Form	Record whether family/friend was involved in the treatment	After each session; both PREVENT and EUC participants
Goal Satisfaction Form	Rate participant's level of satisfaction with goals	The session following the one in which a new goal was formulated or revised
Incident Hospitalization/ED Visit Form	To gather information on hospitalizations and ED visits that occurred after the index ED visit	Any time that the CHW learns of a hospitalization/ED visit after the index visit; both PREVENT and EUC participants
Initial Team Contact Form	To inform the PCP and nurse that the participant was randomized to active intervention and to collect preliminary information about the participant	Prior to session 1
Interventionist Adherence Rating Form	CHW's ratings of participant's engagement with the intervention	After 6 th initial session and last booster session
Interventionist Communication Log	Record all phone calls and EMR communications	Every time there is an email, phone, or EMR communication regarding the participant; both PREVENT and EUC participants
Master Goal Log	Document progress with treatment goals	Every time a goal is made, revised, or evaluated
Materials Log	Record all materials dispensed to participant (e.g., glucometer, pedometer, divided plate)	Every time materials are given to the participant
Missed Visit Log	Record reasons for missed visit	Every time a visit is missed both PREVENT and EUC participants
Out of Window Visit Log	Record visits that occurred out of window	Every time a visit is out of window both PREVENT and EUC participants
Participant Information Form	Provide background information on newly randomized participants to interventionist	Given to CHW when a participant is randomized to PREVENT
Referral Log	Record any referrals made to study participants	Every time CHW makes a referral to the participant; both PREVENT and EUC participants
Satisfaction with Telehealth visits	Rate participant's perceptions of the telehealth visits	After the 6th session and the last booster session via phone calls from study staff

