8.2. Preservation of masking

This is a single-masked trial. The Outcome Assessor will be masked to treatment assignment. The PI, participants, the Project Director, the Study Coordinator, the CHW interventionists, the diabetes nurse educator, and PCPs treating participants randomized to PREVENT will be unmasked. Since this study is testing a behavioral intervention and there are no anticipated risks associated with study participation, there are no circumstances in which there will be unmasking based on untoward medical events.

An unavoidable aspect of behavioral intervention research is that participants are aware of their treatment assignments. Several measures will be undertaken to preserve the integrity of masking. First, the Outcome Assessor, who assesses all outcomes, will have no knowledge regarding treatment assignment. Masked staff will not have access to any data files or charts that contain information on treatment assignment. Hard copies of data will be stored in a locked, secure file room at Jefferson. Electronic copies will be stored on an encrypted, password protected server. Second. prior to performing any assessment, the Outcome Assessor will emphasize to all participants the importance of not revealing their treatment assignment. They will be instructed to call the Study Coordinator should they have any questions about this. Third, the Outcome Assessor and the CHW interventionists will be instructed to never discuss any of the participants with each other, either generally or specifically. Fourth, for quality control purposes, after each follow up assessment, the Outcome Assessor will be asked to indicate his/her best guess of which study group the participant is in, as well as his/her reasons for this estimate. If at any time the Outcome Assessor learns of a participant's treatment group, he/she will notify the Study Coordinator immediately, and she will document it so that statistical analyses can be adjusted accordingly. The biostatistician will specifically examine whether unmasking leads to the introduction of treatment-related biases in all reporting of study results. In addition, a research assistant who works in the PI's lab and is employed by the Department of Neurology at Jefferson, will be trained to conduct the follow-up assessments. If a participant's treatment assignment is revealed to the Outcome Assessor, the research assistant will conduct that particular participant's subsequent follow-up assessments.

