8.5. Attrition

The following strategies will be implemented to maximize retention. 1) All participants (in both treatment groups) receive diabetes educational materials. 2) All participants receive \$20 and certificates of completion for all outcome assessments. 3) Established relationships with PCPs will convey credibility to participants and sustain research engagement. 4) We will mail birthday cards and a quarterly "Question-and-Answers" newsletter to all participants to maintain positive, personalized contact. 5) We will make reminder calls the day before in-home appointments, and maintain flexibility when scheduling them. 6) We will have a dedicated telephone line for participants to call for study-related questions.

9: DESCRIPTION OF INTERVENTIONS

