- Session 3: This session will begin with the telehealth visit with the DM nurse educator, who will discuss the participant's current experiences with DM self-care and will target a participant-selected DM self-care goal. Using DM-Specific Behavioral Activation, the DM nurse educator, CHW, and participant will devise an Action Plan for that activity. For diet, an Action Plan might target healthy food choices, food portions, timing meals, and discussing dietary needs with family. The CHW will provide skills training as needed (e.g., plate method to organize meals, using a glucometer). The Action Plan goal might be to reduce soft drink consumption or eat 3 vegetables daily. The Action Plan steps specify the "how, when, and where" of the plan, and are observable, quantifiable. integrated into daily routines, and attainable (to provide positive reinforcement). An Action Plan for exercise (e.g., "walk with a friend") might be: 1) call a friend; 2) pick a date/time; and 3) use a pedometer (supplied) to track distance walked. These steps are recorded on a large print calendar to provide cues to action. Over the next week, the participant will record the number of times the Action Plan is completed, and will rate their sense of accomplishment (to enhance reward salience). The CHW will also anticipate negative perceptions (e.g., "I can't do this" or "This will never work") and encourage the participant to "make room" for these thoughts while still following the Action Plan (i.e., "Follow the plan instead of the feeling").
- Sessions 4-6: The CHW and participant will review previous Action Plans. The CHW will reinforce attained DM self-care goals, help set new ones, and facilitate access to upcoming PCP clinic visits [e.g., discuss barriers (e.g., transportation) and health beliefs (e.g., "check-ups aren't really necessary."); rehearse questions for PCP; and mark upcoming appointments on a calendar]. If a participant has an ED visit and/or hospitalization during treatment, [name] and the CHW will identify modifiable predisposing or precipitating factors, and develop an Action Plan to address them. Session 5 will include the 2nd telehealth visit with the DM nurse educator to answer questions, identify treatment barriers, and set new DM self-care goals. After session 6, the CHW will upload the current CHW Encounter Form for the PCP's review.

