10.2 Adverse Event and Serious Adverse Event Collection and Reporting

10.2.1. Alerts and Serious Adverse Events

An adverse event (AE) is any unfavorable and unintended diagnosis, symptom, sign (including an abnormal laboratory finding), syndrome or disease which either occurs during the study, having been absent at baseline, or if present at baseline, appears to worsen. Adverse events will be reported regardless of their relationship to the study intervention.

A serious adverse event (SAE) is any adverse event that results in death, is life threatening, or places the participant at immediate risk of death, requires or prolongs hospitalization, causes persistent or significant disability or incapacity, or any other condition which the PI or DSMB judges to represent significant hazards.

All AEs and SAEs will be reported regardless of their relationship to the study intervention.

Solicited AEs and SAEs will be detected at the follow-up assessments to occur at 6 and 12 months. The Outcome Assessor will use a structured questionnaire to inquire about hospitalizations, emergency room visits, surgeries, and physician visits. The Outcome Assessor will also assess depressive symptoms and suicidal ideation. In addition, every 6 months staff will review participants' medical charts to identify new medical diagnoses, emergency department visits, and hospitalizations.

Unsolicited AEs and SAEs will be detected when participants spontaneously report a medical event during a phone call or a PREVENT or EUC treatment session.

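### The masking safeguards do not cover PREVENT materials that the Outcome Assessor may see in the home, so the arm can be learned by sight at the visit where this first happens

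*Combined protocol and SAP*

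**What the plan says.** Section 3.2 places the Outcome Assessor's work at "follow-up assessments at 6 and 12 months in participants' homes masked to treatment assignment". Section 8.2 is categorical: "the Outcome Assessor, who assesses all outcomes, will have no knowledge regarding treatment assignment".

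The same manual describes items linked to one arm:

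- Section 4.3 lists, among the costs that the trial covers, "supplies to assist with the achievement of treatment goals for PREVENT participants (e.g., glucometers and supplies, pedometers".
- The Treatment Process Data table in 6.2 has a Materials Log whose purpose is "Record all materials dispensed to participant (e.g., glucometer, pedometer, divided plate". The table's title limits each form to PREVENT unless a row says otherwise, and this row does not.
- Section 9.1, Session 3, says of the Action Plan: "These steps are recorded on a large print calendar to provide cues to action". Section 9.2 excludes Behavioral Activation and telehealth from EUC.

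On questioning, 10.2.1 states: "The Outcome Assessor will use a structured questionnaire to inquire about hospitalizations, emergency room visits, surgeries, and physician visits".

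Section 8.2 sets out the safeguards. First among those involving participants, "the Outcome Assessor will emphasize to all participants the importance of not revealing their treatment assignment". The assessor also has no access to files showing the arm, does not discuss participants with the health workers, records a best guess of the arm with reasons after each follow-up, and reports any unmasking. Unmasking is documented, a substitute does that participant's later assessments, and the biostatistician examines bias. Section 9.2 gives both arms home visits and matched educational materials. Appendix 4 repeats the request not to tell and the duty to report.

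Section 8.5 already provides a contact before each home visit: "We will make reminder calls the day before in-home appointments".

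**The concern.** The safeguards act on what participants say and on what is done once unmasking is known. They do not act on what the assessor can see. The follow-up visits fall after treatment has begun, and PREVENT boosters at months 6, 8 and 10 mean that materials may still be in use. Section 7.1 requires every team member to read the manual that links these items to PREVENT. Appendix 4 has the assessor ask to see medication bottles, and the self-care scale covers glucose monitoring, exercise and diet, so participants may well bring out such items.

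If the assessor infers the arm, probing or recording could differ by arm. The scales exposed are the PSQ-18 and the DSCI-R (Secondary Aims 1 and 3, and two of the three mediators in Aim 4), the PHQ-9, quality of life and health beliefs. Elicitation of ED visits outside the record system is exposed too, since Appendix 10 notes that Epic may miss out-of-network visits.

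**Working it through.** **Routes to unmasking, set against the safeguards**

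| Route | Safeguard | Gap |
|---|---|---|
| Participant states the arm | Request not to tell (8.2, Appendix 4) | Covered as far as a request can |
| Files or staff conversations | No file access, no discussion with health workers (8.2) | Covered |
| Home visits as such | Both arms have them (9.2) | Covered |
| Pedometer, divided plate or calendar seen | Guess, reporting, later substitution, bias examination (8.2) | Detected or handled afterwards, not prevented |
| Answer to the physician-visit question | Request not to tell | Partly open: reveals the arm only if study telehealth or the health worker is described |

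**What substitution covers.** A participant unmasked at month 6 has the substitute at month 12, which is the time point tested for Secondary Aims 1 to 3. Two cases remain: the month-6 visit at which unmasking occurs, and first unmasking at month 12.

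**Size.** The plan gives no figure to reproduce, and no unmasking rate. The calculation below is illustrative.

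Inputs:

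- 78 randomized per arm, 156 in total (section 5.1).
- Test: group difference in change from baseline to month 12, from a mixed model with time, arm and their interaction (section 13.1.1, Secondary Aims).
- Assumed: half of PREVENT visits unmasked, with scores then shifted by 0.1 to 0.2 SD. The bias is b = 0.5 × 0.1 = 0.05 SD to 0.5 × 0.2 = 0.10 SD.
- Assumed: baseline to month-12 correlation r = 0.5, equal variances, complete data.

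Standard error of the difference in change, in SD units:

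SE = (2/√156) × √(2(1 − r)) = 0.160 × √1 = 0.160

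Two-sided error at nominal 5%:

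P(Z > 1.96 − b/SE) + P(Z < −1.96 − b/SE)

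- b = 0.05: b/SE = 0.312; 0.0497 + 0.0115 = 0.061.
- b = 0.10: b/SE = 0.625; 0.0909 + 0.0049 = 0.096.

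Sensitivity to the assumed correlation:

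| r | SE (SD) | b = 0.05 | b = 0.10 |
|---|---|---|---|
| 0.3 | 0.189 | 5.8% | 8.2% |
| 0.5 | 0.160 | 6.1% | 9.6% |
| 0.7 | 0.124 | 6.9% | 12.7% |

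A baseline-adjusted contrast would have the smaller SE, (2/√156) × √(1 − 0.5²) = 0.139, and would give 6.5% to 11.1% at r = 0.5. That is not the contrast that the plan tests.

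**The case against.** The strongest reply is that the plan foresees unmasking and handles it in several ways. The guess is recorded with reasons, so visual cues would come to light. The duty to report applies whatever the route. Differential coding is limited: the computer prompts each question and answers are entered directly (12.1), every recording is compared with the database (12.4), and 10% of assessments are reviewed (8.4). Participants know their arm anyway, so assessor masking cannot remove all self-report bias. All of this stands. It reduces the consequences of unmasking but does not stop the assessor from seeing the items.

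The visual evidence also has limits. No section says that EUC homes lack these items; that is a strong inference from 4.3, the Materials Log and the content of EUC. A glucometer alone says little about arm in people with diabetes. PREVENT goals are chosen by the participant, so not every PREVENT home need hold a pedometer or a divided plate, and everyone receives plate-method leaflets (6.3). The manual calls the calendar a cue to action but does not say where it is kept.

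Three stronger readings are tempting and are not supported:

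- A reader might infer that the substitute never protects month 12. Under 8.2 it does so for anyone unmasked at month 6.
- A reader might infer that the physician-visit question gives the arm away. EUC includes usual primary care, so both arms report such visits.
- A reader might infer that all outcomes are at risk. HbA1c is a device reading, Quality Metrics come from records, records are searched for events in all participants, and masked physicians classify the events (6.2).

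**Conclusion.** The point holds as a gap in prevention. The assessor's ignorance of the arm is stated without qualification, yet no safeguard addresses PREVENT items visible in the home, and the visit at which unmasking first occurs is unprotected, including a first unmasking at month 12. The question about physician visits is a lesser route.

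The reach is limited mainly to the self-report scales that the assessor administers and to elicitation of out-of-network events. Quality Metrics, HbA1c and event classification are largely protected.

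The size is unknown. An error of about 6.1% to 9.6% follows only if the bias is 0.05 to 0.10 SD and the correlation is 0.5, neither of which the documents supply. A reader should not infer that the trial's error rate is in fact inflated by that amount. The case for acting rests on the low cost of the remedy, not on this figure.

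**What to change.** In 8.2 and Appendix 4:

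1. Use the existing day-before reminder call, with the same script for both arms, to ask every participant to put study materials and calendars out of sight and not to name or describe their health worker.
2. Ask the utilization and adverse-event questions after all self-report scales, with their content unchanged.
3. Record the assessor's arm guess, with reasons, both before and after those questions.

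The cost is a slightly longer call and a reordering of REDCap forms. No extra staff are needed.

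Two further changes are not advised. Rewording the questions to leave out visits arranged by the study would alter adverse-event capture and could prompt disclosure. A separate list of due dates for the assessor is largely provided by 6.4.

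The documents say that recruitment ended early but not whether follow-up is complete. If it is, these steps come too late. What remains is to report the recorded guesses and reasons by arm and to specify the analysis of unmasking bias that 8.2 promises and section 13 does not describe.
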